4.2 SUMMARY OF MAJOR ENDPOINTS

Primary endpoints:

Acceptability

- The proportion of participants who report willingness to use the study regimen, take up PrEP and remain on PrEP as part of a comprehensive prevention package.

- Assessment of acceptability as per questionnaire administered at study end.

Use

- Number of adolescents who continue to use PrEP (as indicated by DBS/ plasma levels) after the initial 3 month period
- The total time on PrEP for each adolescent (as indicated by DBS/plasma levels) and for the cohort as a whole in those individuals who indicated PrEP use by self report at the beginning of each 3 month period.

Safety

- Grades 2, 3, and 4 clinical and laboratory adverse events;

Secondary endpoints:

Adherence:

- Adherence to daily regimens of oral PrEP as evidenced by the use self-report, pill counts, and proportion of participants on FTC/TDF who have detectable drug levels. Proportion of blood samples with detectable drug levels
- Proportion of adolescents with detectable drug levels who report using PrEP
- Proportion of doses that are taken as instructed.

Sexual and other Behaviors

- Reported number of steady and casual sex partners, condom use (and change after introduction of study product), substance use prior to or during sex, as evidenced by participant responses to interviewer-administered questionnaires and focus groups.
- Proportion of scheduled HIV testing appointments missed, in relation to individual characteristics (age, sex, number of partners, use of other prevention methods) and the characteristics of the product.

HIV infection,

- as measured by seroconversion of study participants during the approximate 12 months of follow-up.

Exploratory endpoints:

Impact on adherence of providing information on drug (FTC/TDF) levels (as measured in Dried Blood Spot/Plasma) given as feedback during counseling sessions.

- Number of counselling opportunities in which drug level feedback is requested vs total number of counseling events
- Number and nature of participants who request drug level feedback.
- Correlation between self reported adherence and drug levels at each visit for each participant
- Correlation between self reported adherence and drug levels at each visit in the study overall.
- Proportion and number of participants whose adherence to study product improves when receiving the results of DBS/Plasma compared to those who do not receive feedback of results as measured by endpoints above.

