7.4 FOLLOW UP VISITS (AFTER WEEK 13 AND UP TO WEEK 48; VISITS AT 24, 36, 48)

For the initial product usage lead-in period (Weeks 4-12), study participants will be asked to adhere to the study product. After the 12 week lead in period, participants will be asked at subsequent 12 weekly visits whether they wish to continue PrEP, stop PrEP or restart PrEP as part of their prevention package (Week 12, 24 and 36). All participants regardless of product usage will be followed for the duration of the study. Participants will be advised to make these decisions at scheduled study visits. Reasons for decision will be enquired upon and recorded in CRFs.

Participants will also however be told they can contact study site at any time and also when they should with-hold PrEP for medical reasons.

Participants will complete scheduled 4 weekly follow-up visits until week 12. Thereafter, all visits will be 12 weekly regardless of PrEP addition to the prevention package or not. Target dates are set based on the enrollment date, and do not change if subsequent actual visits take place before or after the target date.

As it will not always be possible to complete follow-up visits on the targeted dates, follow-up visits may be completed within an approximate 2-week window around the target date (-/+7days from the target date).

The following procedures will be completed at each Follow-Up Visit (wks 24, 36, 48):

- Administrative/Behavioural Procedures
 - Locator information (update)
 - At all visits
 - HIV pre-and post-test counseling, including risk reduction counselling
 - At all visits
 - Social harms and/or benefits
 - At all visits
 - Sexual risk behavior questionnaire

- At all visits
- Provision of condoms
 - At all visits
- Provision of study drug (for participants who choose to receive study product)
 - at visits Wk 12, 24, 36 .
- Acceptability assessment
 - at visits Wk 12, 24, 36, 48.
- Adherence Counselling (if participant is on study product)
 - at visits Wk 12, 24, 36, 48 (week 48 visit will be feedback on last 3 months only since no more product will be offered).
- Feedback of plasma drug level/DBS results (to participants on study product who agree to receive this information at the time of adherence counseling.)
 - At visits Wk 12, 24, 36, 48.
- Adherence assessment (including pill counts) and counselling (for participants who choose to receive study product)
 - At visits Wk 12, 24, 36, 48

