7.5 INTERIM VISITS

Participants may make interim contacts and unscheduled visits at their request, or as deemed necessary by the Site Investigator or designee, at any time during the study. All interim contacts and unscheduled visits will be documented in the participant's study file. When an interim contact or unscheduled visit occurs in response to AEs, a study clinician will clinically assess the reported

event and provide, or refer the participant for, appropriate medical care. Study participants will be instructed to contact their study clinic in the event of any AE. Participants will also be instructed to seek immediate emergency care (even from other providers) if they consider they require it. The AE will be reported on the appropriate CRF.

Some examples of reasons for an interim visit are:

- To report an AE;
- To get more condoms or study product;
- To address any contraceptive needs;
- To ask questions of study staff;
- To discuss problems with study adherence;
- To perform an interim examination (e.g., follow-up on an AE or participant request); and
- To provide lab results not available at the last follow-up visit.

If a participant is contacted when s/he missed a visit, staff will try to obtain her reasons for missing a visit. This information may be used to try to improve overall retention in the study.

7.6 FINAL STUDY VISIT (WEEK 52) OR TERMINATION VISIT (AND AT THE TIME OF ANY PERMANENT STUDY PRODUCT TERMINATION OR STUDY PRODUCT DISCONTINUATION)

Participants who reach week 52 will follow procedures included in the table of study procedures on page 72. This includes provision of any outstanding test results and final interviews. In addition a DBS/ plasma will be performed for drug levels at the final study visit.

Participants who have chosen to discontinue the product prior to the routine protocol-required withdrawal at Week 52 should continue routine follow-up visits. All protocol-required interviews and procedures, besides study product administration and drug levels, should be continued until Final Study Visit.

If a participant discontinues study product following instruction from the Investigator or wishes to withdraw permanently from the study, visit procedures as per week 48 will be conducted. The participant will then return for a final study visit (week 52) if possible.

The following procedures will be completed the final visit (wk 52 the final visit):

- Administrative/Behavioural Procedures
 - Locator information (update)

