7.12 BIOHAZARDOUS WASTE

The Principal Investigator will ensure that biohazardous waste will be contained according to institutional, transportation/carrier, and all applicable regulations.

Table1: Schedule of Study Visits and Procedures**Nb. Screening visit (up to -4 weeks); Enrollment (0 weeks); Final visit (52 weeks).**

Visit week	Prior	Screening	Enrolment	4	8	12	24	36	48	Final 52
Obtain written informed consent for screening and enrolment, from participant and his/her guardian		X								
Assessment of understanding for ICF		X								
Identification number assignment		X								
Locator information		X	X	X	X	X	X	X	X	X
HIV pre-and post-test counselling		X	X	X	X	X	X	X	X	X
Eligibility assessment (including review of all screening documentation)			X							
Sexual risk behavior questionnaire			X	X	X	X	X	X	X	X
Acceptability questionnaire				X	X	X	X	X	X	X
Adherence assessment and counselling				X	X	X	X	X	X	
Feedback of DBS or plasma results to those who agree to this.				X	X	X	X*	X*	X*	
Provision of condoms, condom counselling and rest of prevention package (bar PrEP)		X	X	X	X	X	X	X	X	X
Study product supplies and instructions *Only to those who indicate willingness to use.			X	X	X	X*	X*	X*		

Visit week	Prior	Screening	Enrolment	4	8	12	24	36	48	Final 52
Reimbursement	X	X	X	X	X	X	X	X	X	X
Schedule next visit (if applicable)		X	X	X	X	X	X	X	X	*
Focus group (including assent/consent)	X									X
Obtain/update medical history		X	X	X	X	X	X	X	X	X
Conduct physical exam		X	*	*	*	*	*	*	X	*
Incl TS at enrollment and week 48										
Disclose available test results		X	X	X	X	X	X	X	X	X
Provide or refer for contraception		X	X	X	X	X	X	X	X	*
Contraceptive counseling		X	X	X	X	X	X	X	X	X
Record/update AEs including social harms/benefits			X	X	X	X	X	X	X	X
Treat or prescribe treatment		*	*	*	*	*	*	*	*	*
Syndromic treatment for STIs										
Hepatitis B sAb/sAg testing		X								
Hepatitis B vaccination		*	*				*			
HIV serology		X	X	X	X	X	X	X	X	X
Herpes (HSV-2)		X				X			X	
Chlamydia, and Gonorrhea testing.										
Females low vaginal self-swab		X				X			X	
Males Urine										
Serum chemistries		X				X	X	X	X	
Creatinine Clearance										X
ALT/AST serology		X				X	X	X	X	X
Haematocrit				X	X					X
Full Blood count		X				X	X	X	X	
Measurement of study drug levels (DBS and plasma for drug levels)				X	X	X	X #	X #	X #	X #
Measurement of study drug levels by DBS only										X #

Visit week	Prior	Screening	Enrolment	4	8	12	24	36	48	Final 52

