The DTHF protocol and research teams hypothesize that oral once daily PrEP (TDF/FTC) will be acceptable and utilized safely by healthy adolescents, between the ages of 15-19 years.

SAMPLE SIZE CONSIDERATIONS

The sample size calculation is based on the ability to detect the measure the primary

CHAMPS: Choices For Adolescent Prevention Methods for SOUTH AFRICA

Pilot study B: “PlusPills”

A Demonstration Open Label Study to Assess the Acceptability and Use of Truvada Pre-exposure Prophylaxis in Healthy, HIV-Uninfected Adolescents, 15-19 Years of Age.

objectives (acceptability and use) in the participant population. The table below shows the precision (as 95% confidence limits) provided by various sample sizes in detecting the occurrence of acceptability endpoints (with a frequency non- uptake and use varying from 5%-20%).

Acceptability will be measured by proportion of youth who take up PrEP and remain on PrEP as part of a comprehensive prevention package. Also they will complete an acceptability questionnaire.

	Precision *		
Frequency	n=100	n=135	n=170
5%	1.6; 11.2	2.1; 10.4	2.4; 9.8
10%	4.9; 17.6	5.7; 16.8	6.4; 16.2
15%	8.6; 23.5	9.9; 22.8	10.7; 22.2
20%	12.7; 29.1	14.2; 28.6	15.3; 28.1

* Asymptotic (exact) binomial 95% confidence limits

Based on these calculations, we anticipate that 135 participants, rounded up to 150 participants to account for premature censoring (due to loss to follow-up and/or withdrawal of consent, estimated at maximum 10%) will be required to detect non-acceptability endpoints that occur in 10% of subjects with approximately 5% precision.

DATA AND SAFETY MONITORING AND REVIEW

In addition to the informal safety monitoring done by the Site Investigator and study clinician, DTHF will convene an independent Protocol Safety Review Team (PSRT). The roles of the PSRT are:

CHAMPS: Choices For Adolescent Prevention Methods for SOUTH AFRICA

Pilot study B: “PlusPills”

A Demonstration Open Label Study to Assess the Acceptability and Use of Truvada Pre-exposure Prophylaxis in Healthy, HIV-Uninfected Adolescents, 15-19 Years of Age.

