participants remaining on PrEP, accounting for censoring due to loss to follow-up. We will (i) examine the reasons for discontinuation and (ii) examine the baseline and/or pre-LTF characteristics of those LTF, and compare to those retained, in order to understand the possible associations between LTF and adherence and/or sexual risk taking. While our preliminary analyses will presume this censoring is uninformative, we will include analyses that assume LTF are non-adherent. Our intention is to (i) examine the reasons for discontinuation and (ii) examine the baseline and/or pre-LTF characteristics of those LTF, and compare to those retained, in order to understand the possible associations between LTF and adherence and/or sexual risk taking. While our preliminary analyses will presume this censoring is uninformative, we will include analyses that assume LTF are non-adherent. In subsidiary analyses for this primary endpoint, we will also examine the factors associated with PrEP willingness, uptake and “remaining on PrEP” using standard methods (including chi-square and exact tests for the comparisons of proportions, and log-rank tests for the comparison of ‘survival’ curves in product-limit analysis).

2. Primary: Acceptability

An acceptability questionnaire will be administered 3 monthly to assess reasons for continuing, stopping or restarting PrEP. A further questionnaire will be administered at the final study visit to assess the delivery of PrEP and the content of the study visits, including the user-friendliness of the medication regimen (including an assessment of side effects), the delivery format, the dosing strategy, and the clinic visit schedule.

Analysis Plan:

This acceptability questionnaire will contain both binary items as well as continuous (interval) measures from Likert-type items. Analysis of data from this questionnaire will begin with standard descriptive statistics for each item, overall and by key participant subgroups (a priori, these will be based on participant age, gender, sexual activity during the study and PrEP adherence during the study). We will compare responses to acceptability items using standard methods, including chi-square and exact tests; Student’s t- and rank-

CHAMPS: Choices For Adolescent Prevention Methods for SOUTH AFRICA

Pilot study B: “PlusPills”

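### The study-end acceptability questionnaire, one of the primary acceptability endpoints, is tied to week 52 and has no plan for participants who leave before then

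*SAP*

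**What the plan says.** Protocol 4.2 lists two primary acceptability endpoints. The first is behavioural: willingness, uptake and remaining on PrEP. The second is "Assessment of acceptability as per questionnaire administered at study end". Protocol 10.2 and the SAP endpoint list also place this questionnaire at the final visit.

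SAP A.2 (same text in protocol 10.6) describes two instruments. The first: "An acceptability questionnaire will be administered 3 monthly to assess reasons for continuing, stopping or restarting PrEP". The second: "A further questionnaire will be administered at the final study visit to assess the delivery of PrEP and the content of the study visits". The second also covers the regimen, side effects, dosing and the visit schedule. The planned analysis is item-level descriptive statistics, overall and by subgroup, with standard tests. It names no analysis set, denominator or rule for missing forms.

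Protocol 7.6 says that if a participant "wishes to withdraw permanently from the study, visit procedures as per week 48 will be conducted". The week-52 visit then follows only if it can be arranged.

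SAP A.1 (Use) compares participants lost with those retained and adds an analysis that treats the lost as non-adherent. A.2 has no counterpart. The sample size section allows for "premature censoring (due to loss to follow-up and/or withdrawal of consent, estimated at maximum 10" per cent.

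**The concern.** The study-end form is the only planned source for views on delivery, dosing and visit burden as a whole. Someone lost without contact never receives it. Someone who withdraws formally receives the week-48 set, which on the A.2 wording carries the other form. If participants who dislike the visits or the regimen leave more often, their answers are missing from an endpoint meant to capture them.

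The plan recognises this kind of dependence elsewhere. A.1 looks for links between loss to follow-up and adherence or sexual risk, and A.2 uses adherence and sexual activity as subgroups for the acceptability items. A.1 handles the possibility for Use; A.2 does not handle it for the questionnaire. A reader of the results could not tell how far the item percentages describe the 150 enrolled.

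**Working it through.** **Inputs.** From the sample size section: 135 evaluable, 150 enrolled, loss of at most 10%, planning rate 10% non-acceptability, stated 95% limits at n = 135 of 5.7% and 16.8%. Assumptions made here: a binary study-end item has an unfavourable rate near the planning rate, and all participants lost lack the form.

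**The plan's own figures.** 135 / (1 − 0.10) = 150, as stated. The half-width at 10% is 1.96 × √(0.10 × 0.90 / 135) = 5.1 points, matching the stated precision of about 5%. Exact limits for 14/135 (10.4%) are 5.8% and 16.8%, within rounding of the table.

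**Bounds over all enrolled.** With x unfavourable among responders and m missing, the all-enrolled rate lies between x/150 and (x + m)/150.

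| Loss | Responders | Unfavourable (exact 95% CI) | Best case | Worst case |
|---|---|---|---|---|
| 5% (assumed) | 142 | 14 = 9.9% (5.5 to 16.0) | 14/150 = 9.3% | 22/150 = 14.7% |
| 10% (plan) | 135 | 14 = 10.4% (5.8 to 16.8) | 14/150 = 9.3% | 29/150 = 19.3% |
| 10% (plan) | 135 | 27 = 20.0% (13.6 to 27.7) | 27/150 = 18.0% | 42/150 = 28.0% |
| 20% (assumed) | 120 | 12 = 10.0% (5.3 to 16.8) | 12/150 = 8.0% | 42/150 = 28.0% |

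**Between the extremes.** With loss L, responder rate r and rate q among the missing, the all-enrolled rate is (1 − L)r + Lq, so responders understate it by L(q − r). With L = 10% and r = 10%:

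| q | All-enrolled rate | Understatement (points) |
|---|---|---|
| 5% | 9.5% | −0.5 |
| 10% | 10% | 0 |
| 20% | 11% | 1 |
| 30% | 12% | 2 |
| 50% | 14% | 4 |
| 100% | 19% | 9 |

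**When it would leave the responders' interval.** In the 14/135 case, 11 of the 15 missing unfavourable gives 25/150 = 16.7%, inside the upper limit of 16.8%. Twelve of 15 gives 26/150 = 17.3%, outside it. At the planned loss, about 80% of the missing must answer unfavourably.

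**Which form is given when.** A.2 separates two instruments. The schedule of events has a single row, "Acceptability questionnaire", marked at weeks 4, 8, 12, 24, 36, 48 and 52. Protocol 7.4 lists an "Acceptability assessment" at weeks 12 to 48, and 7.6 uses the same term for week 52. Section 7.6 is headed as covering final and termination visits, yet its text sends withdrawers to the week-48 set. These places do not settle whether a withdrawer sees the study-end form.

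**The case against.** The strongest reply is that much of acceptability is already protected. The sample size section names uptake and remaining on PrEP as the acceptability measure, and that endpoint has exact intervals, product-limit methods and both analyses of loss. Participants who stop PrEP stay in follow-up to week 52 (protocol summary, 7.6), so disliking the pill does not by itself remove someone from the study-end form. Acceptability is also asked from week 4 to week 48 and at the withdrawal visit. The operational sections may even intend one form throughout.

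Most of this stands. A reader might infer that acceptability as a whole is a completers-only estimate; the behavioural endpoint shows that it is not. A reader might also infer that the result will be too favourable. The documents give no acceptability rate for those who leave, so the direction is an assumption. Nor can an interval in A.2 be called wrong, because A.2 plans none.

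What the reply does not answer is narrower. The earlier answers exist, but A.2 does not plan to use them for this purpose, and the documents do not show that the two forms share items. Participants who leave the study itself, for example because of visit burden, remain unrepresented in the study-end items.

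**Conclusion.** The point holds for the study-end questionnaire only. On the SAP and 7.6 wording, its item results rest on those who attend week 52, and nothing in A.2 shows how sensitive they are to loss. That the analysis uses only the forms received is inferred from the absence of any other rule.

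At the plan's maximum loss and planning rate, the possible range is 9.3% to 19.3% against an observed 10.4%. The largest understatement is about 9 points, and a moderate assumption (half of the missing unfavourable) gives 4 points, close to the 5.1-point half-width but inside the interval. If loss were 20%, an assumption beyond the plan, the range would be 8.0% to 28.0%. These figures assume a binary item; Likert items would need a pre-specified cut. The gap calls for a defined analysis and a small procedural change. It does not undermine the other primary endpoints or the sample size of 150.

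**What to change.** 1. In protocol 7.6, give the study-end questionnaire at any withdrawal or termination visit.
2. Reconcile A.2 with protocol 7.3, 7.4, 7.6 and the schedule of events, so that each visit names the form used.
3. In SAP A.2 and protocol 10.6:
   - report the number answering out of 150 for each item;
   - compare the week 4 to 48 acceptability answers of participants lost with those of participants retained;
   - for binary items, or pre-specified dichotomies of Likert items, add a sensitivity analysis over all enrolled with best- and worst-case bounds, the worst case counting missing answers as unfavourable.
4. Do not carry earlier answers forward unless the forms are shown to share items.

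The cost is one form at an existing visit and a few extra tabulations. The sample size does not change.
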